4.3 Safety Endpoints

4.3.1 Adverse Events

All adverse events (AEs) and serious adverse events (SAEs) will be reported by the investigator as specified in Section 8 in the CSP.

4.3.2 Clinical Laboratory Tests

4.3.2.1 Hematology, Serum Chemistry, Immunology and Urinalysis, Serology

The following samples will be analyzed by the local laboratory.

Hematology with Differential: to include; hemoglobin, hematocrit, red blood cells (RBCs), white blood cells (WBCs), platelet count, WBC subset count (neutrophils, eosinophils, basophils, lymphocytes, and monocytes), mean corpuscular volume (MCV), mean corpuscular hemoglobin (MCH), mean cell hemoglobin concentration (MCHC).

Clinical Chemistry - to include; lipase, amylase, albumin, total protein, blood glucose (non-fasting), sodium, potassium, chloride, bicarbonate, magnesium, calcium, blood urea nitrogen

(BUN), creatinine, AST, ALT, alkaline phosphatase (ALP), total bilirubin, direct bilirubin, lactate dehydrogenase (LDH), gamma glutamyltransferase (GGT), and phosphate, thyroid function testing (triiodothyronine (T3) or free triiodothyronine (FT3), Thyroxine (T4) or free thyroxine (FT4), TSH).

Immunology: to include CD3, CD4, CD8 and CD19

Urinalysis – Urine collected to determine pH, blood, protein, ketones, leukocyte elastase, nitrite, glucose, specific gravity, urobilinogen, and bilirubin. If blood, leukocytes or nitrites are detected, microscopy will be completed.

Serology: to include Hepatitis C Antibody

4.3.2.2 Pregnancy Testing

For women of childbearing potential, the following tests are performed:

- At screening: serum β -HCG pregnancy test (a negative test is required to confirm eligibility).
- Before dosing on Days 1 of each cycle: urine pregnancy test (a negative test is required before dosing).

4.3.2.3 Histology

Submission of formalin-fixed paraffin embedded tumor tissue sample blocks are preferred; if submitting unstained slides, the slides should be freshly cut and submitted to the testing laboratory within 7 days from site slide sectioning date otherwise a new specimen will be requested. See laboratory manual.

4.3.3 Physical Examination

The physical examination will include examination of the following: general appearance, head, ears, eyes, nose, throat, neck (including thyroid), skin, cardiovascular system, respiratory system, gastrointestinal system, musculoskeletal system, lymph nodes and nervous system. Any findings made during the physical examination will be noted regardless of if they are part of the patient's medical history.

4.3.4 Vital Signs

Vital signs include sitting blood pressure, heart rate, respiratory rate, and temperature.

4.3.5 ECGs

12-lead ECGs will be taken in the supine position, after the patient has been lying down for at least three minutes.

The following parameters will be assessed: heart rate; PR, QRS, QT, QTcF (Fridericia's correction) intervals. The Investigator (or a qualified observer at the investigational site) will interpret the ECG using one of the following categories: within normal limits, abnormal but not clinically significant, or abnormal and clinically significant.

4.4 Pharmacokinetic Assessments

Pharmacokinetic blood samples will be collected at four different time points during Cycle 1:

- Day 1, 4 hours after completion of birinapant infusion.
- Day 2, 24 hours after completion of birinapant infusion.
- Day 8, before the infusion of birinapant.

- Day 8, 4 hours after completion of birinapant infusion.

See Section 11 in the CSP for more details.

5. Analysis Methods

5.1 Clean File and Timing of Analysis

When the database has been declared to be complete and accurate, the database will be locked and declared clean file. Any changes to the database after that time can only be made by joint written agreement between the project manager, the data manager and the statistician.

The final analysis will be performed after declared clean file, and after finalization and approval of this SAP document.

5.2 Analysis Populations

The analysis of data will be based on different subsets according to the purpose of analysis, i.e. for efficacy and safety respectively. The classification of each patient with respect to each analysis population will be done prior to database lock.

5.2.1 Intent-to-Treat Population (ITT)

Will comprise any patient that is enrolled to the study and receives a dose of pembrolizumab and birinapant. Note that the ITT population can be considered equivalent to the FAS population, which is also the safety population, as no randomization is done in this study.

5.2.2 Efficacy Evaluable Population

Will comprise all patients in the ITT population who have baseline and at least one post-baseline efficacy assessment, unless the patient dies or experiences an AE that results in study drug termination prior to assessment. At that point, the patient will be considered to have progressed in the absence of other data.

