5.6.1 Restricted and prohibited medications

Patients are prohibited from receiving the following therapies during screening and the treatment phase (dose-escalation and dose-expansion) of this study:

- Antineoplastic systemic chemotherapy or biological, immune- or chemotherapy not specified in this protocol;
- Granulocyte-macrophage colony-stimulating factor (GM-CSF)
- Investigational agents other than pembrolizumab and birinapant;
- Radiation therapy
 - Radiation therapy to a symptomatic solitary lesion or to the brain may be considered on an exceptional case by case basis after consultation with Sponsor's Medical Monitor. The patient must have clear measurable disease outside the radiated field. Administration of palliative radiation therapy will be considered clinical progression for the purposes of determining progression.
- Live vaccines within 30 days before the first dose of trial treatment and while participating in the study. Examples of live vaccines include, but are not limited to, the following: measles, mumps, rubella, chicken pox, yellow fever, rabies, BCG, and typhoid (oral) vaccine. Seasonal influenza vaccines for injection are generally killed virus vaccines and are allowed. However, intranasal influenza vaccines (e.g., Flu-Mist®) are live attenuated vaccines, and are not allowed.
- Systemic glucocorticoids for any purpose other than to modulate symptoms from adverse event of suspected immunologic etiology. The use of physiologic doses of corticosteroids may be approved after consultation with the Sponsor's Medical Monitor.
 - Inhaled steroids are allowed for management of asthma.
- Anti-TNF agents are excluded while on study treatment and must be discontinued prior to Cycle 1 Day 1 for a period of 5 half-lives. Examples include:
 - Infliximab (Remicade®)
 - Entanercept (Enbrel®)
 - Adalimumab (Humira®)
 - Certolizumab (Cimzia®)
 - Golimumab (Simponi®)

Patients who, in the assessment by the Investigator, require the use of any of the aforementioned treatments for clinical management should be removed from the study. Patients may receive other medications that the Investigator deems to be medically necessary.

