6.3.2 Disease Progression Follow up Visit

Those patients that are discontinued from study treatment due to reasons other than disease progression, but have not withdrawn consent to be followed for survival; will need to be followed every 30 days until documentation of disease progression or initiation of a new therapy for their disease. Once there is documentation of disease progression or initiation of a new therapy for their disease, the patient will move into the long-term survival follow up phase of the study.

The following procedures will be performed at this follow up visit:

- Hematology, serum chemistry
- ECOG PS
- Radiological tumor assessment (RECIST v1.1 and iRECIST) until documentation of disease progression as defined by RECIST or iRECIST
- Initiation of any new cancer therapy and type of therapy

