8 ADVERSE EVENTS

8.1 Definition of Adverse Events

As defined by the ICH/GCP (CPMP/ICH/135/95), an AE is:

- Any untoward medical occurrence in a study patient administered a pharmaceutical product and which does not necessarily have a causal relationship with this treatment.
- An AE can therefore be any unfavorable and unintended sign (including an abnormal laboratory finding), symptom, or disease temporally associated with the use of a medicinal product, whether or not considered related to the medicinal product.

An AE includes but is not limited to:

- Any clinically significant worsening of a patient's pre-existent condition
- An overdose, whether accidental or deliberate, defined as a dose higher than that prescribed by a healthcare professional for clinical reasons, or a dose higher than that described in the approved labelling for a marketed product, or in available clinical data for a study drug
- Abuse (i.e., use for nonmedical reasons) of an investigational or marketed product

Note: Progression of the cancer under study is not considered an adverse event.

A protocol-related AE is any AE that bears a direct relationship to a study procedure or the alteration of ongoing pre-study drug regimens, medical procedures, or treatments discontinued as required by the protocol.

8.1.1 *Recording and Reporting of Adverse Events*

All adverse events that occur after the consent form is signed but before treatment start must be reported by the investigator if they cause the subject to be excluded from the study, or are the result of a protocol-specified intervention, including but not limited to washout or discontinuation of usual therapy, diet, placebo treatment or a procedure.

From the time of treatment start through 30 days following cessation of treatment, all adverse events must be reported by the investigator. Such events will be recorded at each examination on the Adverse Event case report forms/worksheets. The reporting timeframe for adverse events meeting any serious criteria is described in section Immediate Reporting of Adverse Events to the Sponsor. The investigator will make every attempt to follow all subjects with non-serious adverse events for outcome.

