- For a **clinically stable** subject with first radiologic evidence of progressive disease by RECIST 1.1 (i.e., **unconfirmed progression of disease or iUPD**), it is at the discretion of the site investigator to continue treating the subject with the assigned treatment per protocol until progression of disease (iCPD) is confirmed at least 28 days from the date of the scan first suggesting PD. If radiologic progression is confirmed by subsequent scan then the subject will be discontinued from trial treatment. If radiologic progression is not confirmed by iRECIST per the site, then the patient should resume or continue trial treatment and have their next tumor imaging according to the protocol schedule of every 9 weeks (end of every 3rd treatment cycle) until progression is confirmed at a later timepoint by the site. In applying iRECIST, the appropriate documentation at

each time point must be made (i.e. iSD, iUPR, iUCR). For a more comprehensive and detailed account of the application of RECIST 1.1 and iRECIST for in-study imaging assessments please refer to the imaging guide document Note that RECIST 1.1 must always serve as the primary imaging assessment guide up to the first indication of disease progression after which iRECIST may be used as described.

- Any subject deemed **clinically unstable** should be discontinued from trial treatment at 1st radiologic evidence of PD and is not required to have repeat imaging for PD confirmation.
- In subjects who discontinue study therapy without documented disease progression, every effort should be made to continue monitoring their disease status by tumor imaging using the same imaging schedule used while on treatment (every 9 weeks), until (1) the start of new anti-cancer treatment, (2) disease progression (3) death, or (4) the end of the study, whichever occurs first.

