4.2.3.3 Clinical Benefit Rate (CBR)

The CBR is defined as the percentage of patients with the best measurement of response categorized as CR, PR or SD. Note that SD requires no confirmation as is required for the best overall response of either CR or PR. The first tumor assessment is planned to occur 9 weeks after first dose and therefore, iSD documented at the first assessment would typically qualify as iSD. However, an iSD with actual assessment time less than 6 weeks after first dose will not be qualified as iSD. Patients with no post-baseline tumor assessments are considered to have achieved no clinical benefit.

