5.6.1 Primary Efficacy Analysis

The primary endpoint will be summarized for the Efficacy Evaluable Population in accordance with Section 5.3.

The primary efficacy analysis for each of the three main cohorts in the dose expansion phase of the protocol will be evaluated using Simon’s two-stage design (Simon 1989). The null hypothesis that the true response rate (π) is π_0 will be tested against the one-sided alternative $H_A: \pi > \pi_0$ in each of the three cohorts with π_0 , π_1 , n_1 , n , r_1 and r_2 as in Table 4 as follows. In the first stage, n_1 patients will be accrued. If there are r_1 or fewer responses in these n_1 patients, the cohort will be stopped and the p-value for the test will be reported as not significant (no p-value will be calculated). Otherwise, $n - n_1$ additional patients will be accrued for a total of n patients. The null hypothesis will be rejected if r_2+1 or more responses are observed in n patients.

Table 4 Simon’s two-stage design settings in each of the three main cohorts

Indication	Response rate (ORR)		n_1 (# patient in the 1 st stage)	n (Total #patients)	r_1 (Continue with stage 2 if $>r_1$ responses in stage 1)	r_2 (p-value ≤ 0.05 if $>r_2$ responses after stage 2)
	Poor drug (π_0)	Good drug (π_1)				
Colorectal cancer	$\leq 5\%$	$\geq 20\%$	13	27	0	3

Ovarian cancer	$\leq 7\%$	$\geq 25\%$	16	26	1	4
Cervical cancer	$\leq 10\%$	$\geq 30\%$	15	25	1	5

In case the total number of evaluable patients do not equal the planned number of patients (n in Table 4), the statistical inference of the ORR will take account of the actual total number of evaluable patients, n^* , as suggested in Koyama and Chen (2007). With a modified stage 2 sample size, the p-value will be calculated as follows.

- i. Find π^* such that $P_{\pi}(X_2 > r_2 - x_1 | n_2) = P_{\pi_0}(X_2 \geq x_2 | n_2^*)$
- ii. Compute the p-value by

$$\sum_{x=r_1+1}^{n_1} P_{\pi_0}(X_1 = x | n_1) A(x, n_2, \pi^*)$$

Here $n_2 (= n - n_1)$ denotes the planned number of patients in the second stage, n_2^* the actual number of patients in the second stage and X_2 denotes the number of responses among those n_2 patients. The p-value will be calculated as above even if $n_2^* = n_2$. In that case it simplifies to the original Simon's 2-stage design with rejection regions as in Table 4.

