5.6.5 Sensitivity Analyses

A sensitivity analysis of the primary endpoint will be conducted if there are patients that are wrongly included into the study and receives a dose of pembrolizumab and birinapant. In that case, the primary efficacy analysis will be repeated when those patients are excluded from the efficacy evaluable population, for the cohorts it concerns, as a sensitivity analysis. Also other major protocol deviations may be considered in this sensitivity analysis.

5.7 *Safety Analyses*

No formal statistical analyses will be performed, although descriptive summaries for continuous data and for categorical data will be provided in accordance with Section 5.3 if other not stated. Complete listings of all patient safety evaluations will be provided to support each summary table.

All presentations will be based on the safety analysis set.

5.7.1 *Adverse Events*

Adverse Events (AEs) will be coded by system organ class (SOC), preferred term (PT) and Verbatim name using MedDRA Version 20.0

All AEs will be listed whereas the treatment emergent AEs (TEAEs), i.e. any AE with onset or worsening on or after the first dose of any IMP and within 30 days after the last dose of IMP, will be summarized as follows. The number of TEAEs, as well as the number and percentage of patients reporting any TEAE will be summarised for Cycle 1, subsequent cycles and Safety follow-up by cohort. Separate summary tables will be produced for the following:

1. TEAEs related to IMP by Verbatim names
2. TEAEs related to IMP by SOC and PT
3. TEAEs not related to IMP by Verbatim name
4. TEAEs not related to IMP by SOC and PT
5. Serious Adverse Events (SAEs) by Verbatim name
6. SAEs by SOC and PT.
7. TEAEs related to IMP by AE grade
8. TEAEs not related to IMP by AE grade

AEs leading to withdrawals or death will be presented by cohort.

All percentages will be based on the number of patients in the safety set.

5.7.2 *Clinical Laboratory Tests*

All laboratory parameters for individual patients will be listed and patients with abnormal values (out of normal range reported by the laboratory) and with clinically significant abnormalities (according to the Investigator's criteria) will be flagged.

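### The primary ORR leaves out treated patients who were never scanned unless they died or stopped for an AE, no all-treated ORR is planned, and the safety set contradicts Protocol 12.1

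*SAP*

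**What the plan says.** **Efficacy.** SAP 5.6.1 states: "The primary endpoint will be summarized for the Efficacy Evaluable Population". Under SAP 5.2.2 (and Protocol 12.4) a member of that set must belong to the ITT population and have a baseline and "at least one post-baseline efficacy assessment, unless the patient dies or experiences an AE that results in study drug termination prior to assessment"; patients who meet the death or AE exception are kept as progressed. Protocol 8.1 notes: "Progression of the cancer under study is not considered an adverse event". Missing efficacy values are not imputed (SAP 5.4.1). Secondary and exploratory efficacy use the same set (SAP 5.6.2, 5.6.3). In the one sensitivity analysis (SAP 5.6.5), which concerns wrongly included patients, "the primary efficacy analysis will be repeated when those patients are excluded from the efficacy evaluable population". For CBR, SAP 4.2.3.3 says: "Patients with no post-baseline tumor assessments are considered to have achieved no clinical benefit". There is no matching sentence for ORR.

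**Imaging after early stopping.** Protocol Table 8 schedules a tumor assessment at discontinuation. Patients who stop for reasons other than progression have 30-day visits with imaging "until documentation of disease progression or initiation of a new therapy for their disease" (Protocol 6.3.2). Protocol 9.1.5 adds that, for patients who stop without documented progression, "every effort should be made to continue monitoring their disease status by tumor imaging".

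**Safety.** Protocol 12.4 and SAP 5.2.1 and 5.2.3 equate the safety set with the ITT set, which requires a dose of both pembrolizumab and birinapant. Protocol 12.1 includes anyone given at least one dose of either product. SAP 5.7.1 counts treatment-emergent events from the first dose of any study drug.

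**The concern.** A response needs a scan and a confirming scan at least 4 weeks later (SAP 4.2.3.1), so a patient with no post-baseline scan is a certain non-responder. Removing such patients shrinks the denominator and leaves the numerator unchanged. The exclusion is also likely to be related to outcome, because patients who deteriorate before the first scheduled scan at week 9 are among those at risk of never being scanned.

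The follow-up imaging narrows the gap but does not close it. It ends when a new therapy starts, it rests on best effort, and it cannot reach patients who withdraw consent or are lost. Progression can also be declared without a scan: "Administration of palliative radiation therapy will be considered clinical progression for the purposes of determining progression" (Protocol 5.6.1). The CBR rule shows that the authors accept the principle of counting unscanned patients as failures. Applied to the evaluable set, though, it reaches only those retained by the death or AE clause.

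At stake is the go/no-go test in three cohorts of 26 to 28 patients, where one responder or a few patients in the denominator decide the result.

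On safety, pembrolizumab is infused first on Day 1. Under Protocol Table 7 a Grade 3 or 4 infusion reaction ends study treatment permanently. A patient with such a reaction at the first infusion, before any birinapant, is outside the safety set because of the toxicity. Safety is the primary endpoint of the escalation phase and of the various solid tumors cohort.

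**Working it through.** **Inputs.** SAP Table 4 (colorectal / ovarian / cervical): null ORR 5% / 7% / 10%; target 20% / 25% / 30%; n1 = 13 / 16 / 15; n = 27 / 26 / 25; r1 = 0 / 1 / 1; r2 = 3 / 4 / 5. Planned enrolment is n + 1 = 28 / 27 / 26. The documents do not give the share d of treated patients who are unscanned for a reason other than death or AE, so d is assumed and varied.

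**1. The plan's own figures.** P(reject) = Σ over x > r1 of Bin(x; n1, p) × P(X2 ≥ r2 + 1 − x | n − n1, p).
- Type I error: 0.0416 / 0.0306 / 0.0328, all below the stated 0.05.
- Power: 0.801 / 0.803 / 0.802, against the stated 0.80.

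The design reproduces.

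**2. Direction.** With x responders and m dropped patients, x/(n − m) ≥ x/n, with equality only when x = 0. The inflation factor is 1/(1 − d). Example: cervical 6/26 = 23.1% becomes 6/22 = 27.3% with 4 dropped.

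**3. When the test result changes.** These are p-values by the SAP 5.6.1 method (Koyama and Chen) with a modified stage 2 size. Total responders = r2, with r1 + 1 of them in stage 1 and all dropped patients in stage 2.

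| Cohort | Responders (stage 1) | p, all treated | p, one drop short of the change | p at the change |
|---|---|---|---|---|
| Colorectal | 3 (1) | 0.128 on 28 | 0.053 on 20 | 0.044 on 19 (9 dropped) |
| Ovarian | 4 (2) | 0.090 on 27 | 0.055 on 23 | 0.0464 on 22 (5 dropped) |
| Cervical | 5 (2) | 0.093 on 26 | 0.057 on 23 | 0.0465 on 22 (4 dropped) |

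These are minimum numbers. With one more of the responders in stage 1, the change needs 5 drops in cervical (0.0465 on 21) and 7 in ovarian (0.048 on 20). Colorectal has not changed by 18 evaluable (0.061).

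**4. Type I error.** Of n + 1 treated patients, each is unscanned with probability d and is then a non-responder, so the response rate among evaluable patients under the null is p0/(1 − d). The first n1 evaluable patients form stage 1 and the rest form stage 2. The null is rejected if the SAP p-value is ≤ 0.05, and the result is averaged over the binomial number of evaluable patients.

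| d | Colorectal | Ovarian | Cervical |
|---|---|---|---|
| 0 | 0.046 | 0.035 | 0.039 |
| 10% | 0.047 | 0.038 | 0.043 |
| 20% | 0.049 | 0.052 | 0.061 |
| 30% | 0.058 | 0.061–0.063 | 0.077–0.079 |

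The ranges at 30% reflect how a cohort with n1 or fewer evaluable patients is handled. The 5% level is crossed at d = 21% / 19% / 15%.

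If lost patients were replaced until n were evaluable, the null rate at d = 20% would be 0.05/0.8 = 6.25%, 0.07/0.8 = 8.75% and 0.10/0.8 = 12.5%. Type I error would then be 0.081 / 0.069 / 0.082.

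**5. Safety set.** One missing patient is 1/30 = 3.3 to 1/26 = 3.8 percentage points of incidence in an expansion cohort, and 1/6 = 17 to 1/3 = 33 points in an escalation dose level of 3 to 6. The documents give no first-infusion reaction rate.

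**The case against.** - **The gap is narrow.** A living patient who stopped drug for an AE stays in the set as progressed, and the death clause has no time limit. Protocol 4.3 and 6.1 list deterioration separately from confirmed progression as a reason to stop, so many such patients should enter follow-up imaging. This stands. The clear remainder is withdrawal of consent, loss to follow-up, new therapy before a scan, and clinical progression recorded without a scan.
- **An efficacy assessment need not be a scan.** Protocol 12.7 mentions investigator-judged clinical response. But SAP 4.2.3 bases the analyses on the independent radiologist's category, so this leaves an ambiguity and does not keep these patients in.
- **The direction of bias depends on the benchmark.** If 5%, 7% and 10% are rates among evaluable patients, and scanning is unrelated to response, type I error is not inflated. The documents do not say which denominator those rates use. This stands as a limit on step 4. It does not remove the need for an analysis that would reveal a difference.
- **The design absorbs moderate loss, and replacement is not planned beyond one spare patient.** Both are correct. The step 3 changes are also minima.
- **The all-treated test can cost power.** If 20% / 25% / 30% are evaluable-patient rates and d = 15%, power is 0.70 / 0.69 / 0.68 on all treated patients, against 0.72 / 0.73 / 0.72 on the evaluable set. The difference is small.
- **The safety conflict affects few patients.** They remain in listings, SAE reports and committee review. The summary tables for a primary endpoint would still omit them.

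**Conclusion.** The concern holds on both parts. The primary ORR is computed on a set that removes certain non-responders, and no planned analysis puts them back. Relative to an all-treated ORR the shift can only be upward.

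The size depends on d, which is assumed. At 10% loss the type I error stays under 5% in all three cohorts; at 20% it is 0.052 in ovarian and 0.061 in cervical. These figures take the null rates as all-treated rates. For results near the boundary, 4 exclusions in cervical or 5 in ovarian can be enough to reverse the conclusion. Colorectal is much less sensitive, needing at least 9.

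The safety-set conflict is a direct contradiction between Protocol 12.1 and Protocol 12.4, and the SAP follows 12.4. It should be fixed. It does not invalidate the design.

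**What to change.** 1. Define the primary population for ORR and CBR as all treated patients (at least one dose of either study drug). For ORR, count anyone without a confirmed CR or PR as a non-responder, and use this count for n1 and n in the Simon test. Keep the Efficacy Evaluable Population as a sensitivity analysis. This also makes the CBR sentence in SAP 4.2.3.3 work as written.
2. Align Protocol 12.4 and SAP 5.2.1 and 5.2.3 with Protocol 12.1, so that the Safety Population is every patient with at least one dose of either study drug.

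The cost is protocol and SAP wording, with no extra data. The reported ORR will be slightly lower if there are early unscanned drop-outs. With n + 1 treated patients the test keeps type I error at 0.046 / 0.035 / 0.039 and power at 0.82 / 0.83 / 0.83 when the true all-treated rates are 20% / 25% / 30%. If the sponsor prefers to keep the evaluable set as primary, a prespecified all-treated ORR with unscanned patients as non-responders is the minimum that would make the effect of the exclusions visible.

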4.2.3 Definition of Efficacy Endpoints

All patients will have a tumor measurement after cycle 3 (week 9) and subsequently after every third cycle. Measures will be assessed through RECIST 1.1 until whichever of the following occurs first:

- Site-assessed disease progression is documented
- The start of new anti-cancer treatment
- Withdrawal of consent
- Death
- The end of the study

After progression, measures will subsequently be analyzed through iRECIST as an exploratory endpoint.

The outcome of a tumor measurement for RECIST 1.1 is a categorization into one of the following categories:

- CR – Complete Response
- PR – Partial Response
- SD – Stable Disease
- PD – Progressive Disease
- Non-CR/Non-PD
- Not Evaluable

For iRECIST, a tumor measurement is categorized into one of the following:

- iCR
- iPR
- iSD
- iUPD
- iCPD
- Non-iCR/Non-iPD
- Not Evaluable

Note that RECIST 1.1 and iRECIST is equivalent until Progressive Disease (PD).

There will be two RECIST 1.1 and iRECIST categorizations, one made in the clinic and one made by an independent radiologist at MEDIAN Technologies. The categorization by the independent radiologist is the one that will be used in the analyses detailed in this SAP. The categorizations at the clinic will be reported descriptively as pure explorative purpose.

A tumour measurement may consist of scans conducted at different days (during the visit window) but there will be only one date associated to the categorization for each visit. That date will be set by the independent radiologist and will be the date used in the derivation of the time to event endpoints below. The overall process for image receipt, review and reporting conducted by MEDIAN Technologies is detailed in the Imaging Review Charter -01, dated 7 February 2018.

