4.2.3.2 Progression Free Survival (PFS)

The PFS is defined as the length of time from the start of treatment the patient lives and does not progress (PD as assessed by RECIST 1.1). Patients who do not die or progress will be censored at the date “last known to be alive”, i.e. the latest date of contact with the patient based on all collected evaluation dates.

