5.4 Statistical/Analytical issues

5.4.1 Missing Data and Handling of Dropouts

Missing values will not be imputed/replaced in the efficacy analysis.

Laboratory values which are greater/smaller than a stated value will be replaced by the stated value (for example <1 will be replaced by 1) when summarized in tables.

If the start and/or stop dates for medication, AEs and medical history are unknown the date will be imputed to calculate the duration of AE or to decide if the medication was ongoing at baseline or not. No imputation will be presented in individual patient listings. An unknown date will be imputed as follows:

- If the month and date are unknown, the date will be set to June 30th.
- If the day is unknown, the day will be set to the 15th.
- If the year is unknown, the date will not be imputed.

5.4.2 *Data Transformations and Derived Variables*

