5.6.2 Secondary Efficacy Analyses

The secondary endpoints will be summarized with descriptive statistics in accordance with Section 5.3 for the Efficacy Evaluable Population.

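### A patient stopped for an adverse event before any scan is progressed under SAP 5.2.2 but censored at last contact under the PFS definition, and the plan does not say which rule governs PFS

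*SAP*

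**What the plan says.** Four parts of the SAP meet in one patient.

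- **Population (SAP 5.2.2, repeated in Protocol 12.4).** A treated patient needs a baseline and a post-baseline efficacy assessment to be evaluable, "unless the patient dies or experiences an AE that results in study drug termination prior to assessment". The section then says: "At that point, the patient will be considered to have progressed in the absence of other data". It gives no date for this deemed progression and does not name the endpoints it serves.
- **PFS (SAP 4.2.3.2).** PFS runs from the first treatment for as long as "the patient lives and does not progress (PD as assessed by RECIST 1.1"). The censoring rule in the same section opens: "Patients who do not die or progress will be censored at the date". The date meant is that of the latest evidence of survival, explained as "the latest date of contact with the patient based on all collected evaluation dates".
- **Missing data (SAP 5.4.1).** "Missing values will not be imputed/replaced in the efficacy analysis". No exception is listed.
- **Analysis set (SAP 5.6.2).** "The secondary endpoints will be summarized with descriptive statistics in accordance with Section 5.3 for the Efficacy Evaluable Population". PFS is one of those endpoints in all four expansion cohorts (SAP 4.2.2.2).

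The first scan comes late: "All patients will have a tumor measurement after cycle 3 (week 9) and subsequently after every third cycle". An AE stop in the first two cycles can therefore precede any post-baseline image.

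**The concern.** Take a patient who stops at week 5 for toxicity, is never rescanned, and is still in contact at month 8. SAP 5.2.2 makes this a progression, most naturally dated at week 5. SAP 4.2.3.2 makes it a censored observation at month 8, because an AE stop is neither death nor RECIST 1.1 progression. Both rules apply, since PFS is run on the population that SAP 5.2.2 defines.

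Neither result is a good PFS value. The first records a tolerability failure as tumor growth. The second credits months without imaging as progression-free time, and the patient may by then be on another therapy. The other RECIST and iRECIST time endpoints avoid the second problem by censoring at the last tumor assessment (SAP 4.2.3.4, 4.2.3.5, 4.2.3.10).

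The main cohorts have 26 to 28 patients, so a few such cases can change the published curve and sometimes the median. The outcome would depend on which section the programmer follows.

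**Working it through.** **1. The plan's own figures.** PFS has no planned size or precision. The only sized analysis is the Simon design for ORR (SAP Table 4), stated as type I error 0.05 and power 0.80. The exact rejection probability is the sum over x from r1+1 to n1 of P(X1 = x) × P(X2 ≥ r2 + 1 − x).

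- Colorectal: alpha 0.0416, power 0.8011
- Ovarian: alpha 0.0306, power 0.8029
- Cervical: alpha 0.0328, power 0.8017

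The stated power is reproduced, and the alphas sit below 0.05 as expected for a discrete design. The conflict leaves these unchanged: an unscanned patient stays in the denominator and is a non-responder under either reading. CBR is also settled, because SAP 4.2.3.3 gives no benefit to a patient without a post-baseline assessment.

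**2. Size of the PFS gap.** Let k of n patients be AE stops with no scan and no death. Let S be the week-27 Kaplan-Meier estimate in the n − k scanned patients. Assume no other censoring before week 27 and that the k patients remain in contact beyond it.

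- A, deemed progressed: (n − k)S/n
- B, censored at last contact: [k + (n − k)S]/n
- C, censored at first dose: S

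Then B − A = k/n, whatever S is. The part due to last-contact censoring is B − C = (k/n)(1 − S). The part due to deemed progression is C − A = (k/n)S.

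For n = 27, k/n is 1/27 = 3.7, 2/27 = 7.4 and 3/27 = 11.1 points.

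**3. Simulation for n = 27** (600 cohorts per setting). From the documents: scans every 9 weeks, and a median PFS of 1.9 months (about 8.3 weeks) from the pembrolizumab ovarian cohort cited in Protocol 1.5.2. Assumed: exponential progression, a second median of 18 weeks, stops uniform over weeks 1 to 9, contact to week 54, and the values of k.

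| k | Gap at week 27 | Median differs, true median 8.3 wk | Median differs, true median 18 wk |
|---|---|---|---|
| 1 | 3.7 points | 12.5% of runs | 24.7% of runs |
| 2 | 7.4 points | 29.7% | 43.5% |
| 3 | 11.1 points | 44.3% | 65.5% |

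For k = 3 the week-27 estimates under A, B and C are 9.2%, 20.3% and 10.4% (median 8.3 weeks), and 31.7%, 42.8% and 35.6% (median 18 weeks). The share of the gap due to last-contact censoring is (20.3 − 10.4)/11.1 = 89% and (42.8 − 35.6)/11.1 = 65%.

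**4. Shorter contact.** A second simulation (n = 27, median 2.0 months, stops in weeks 2 to 8, last contact 13 to 52 weeks later, 2,000 runs) gives 6-month PFS under A and B of 22.8% and 26.5% for k = 1, 22.0% and 29.4% for k = 2, and 21.0% and 32.0% for k = 3. Day-1 censoring gives about 24% throughout. The gaps are again close to k/n. The levels are higher because the third scan, at week 27, falls just after 6 months.

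**The case against.** **The trigger is narrow.** This stands. Protocol 6.3.2 asks for follow-up every 30 days with tumor assessment after a stop without progression, until progression or new therapy, and Protocol 9.1.5 asks for continued imaging. A rescanned patient has other data, and a death is an event under both rules. What remains is a patient who starts new therapy, declines imaging or misses visits before any scan. The documents give no rate for this.

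**The sections can be read together.** One could say that a patient deemed progressed under SAP 5.2.2 is not one who has failed to progress under SAP 4.2.3.2, so the specific rule governs. The bracket in SAP 4.2.3.2 requires RECIST 1.1 progression, SAP 4.2.3 takes the category and date from the independent radiologist, and no cross-reference links the sections. This reading is possible but not stated. The SAP 5.4.1 leg is weaker, because SAP 4.2.3.3 also assigns an outcome to unscanned patients.

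**Counting a toxicity stop as failure is conservative.** That is a legitimate choice if declared. The plan does not declare it in the PFS definition.

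**Stronger readings that a reader might infer.** One is that the efficacy conclusion is at risk; it is not, because PFS carries no test (SAP 5.4.4, 5.6). Another is that the reported median typically moves by a scan. That depends on where the true median lies: at 2.5 or 3.0 months, the typical median is week 18 under all three codings for 1 to 3 such patients. A third is that the SAP 5.2.2 sentence causes most of the gap, when last-contact censoring does. Finally, a 6-month PFS rate is not a planned output; SAP 5.3 specifies the Kaplan-Meier plot and the median with its 95% interval.

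**Conclusion.** The conflict is real and confined to descriptive PFS in patients stopped for an AE with no post-baseline scan and no death. ORR, CBR and the Simon decisions are untouched.

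With 1 to 3 such patients of 27, the two codings separate the Kaplan-Meier curve near 6 months by about k/n, roughly 4 to 11 points. About 65% to 90% of that comes from last-contact censoring in the week-27 simulation with three such patients. The planned median differs in a minority of cohorts with one such patient (about 12–25%) and in about half with three (about 44–66%).

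These sizes rest on the assumed counts, exponential progression, deemed progression dated at the stop, and contact continuing well past the stop. The last assumption is most plausible if the survival telephone calls count as contact. SAP 4.2.3.6 includes them for OS; SAP 4.2.3.2 uses the same term without mentioning them.

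The correction is worth making because each rule, followed as written, gives a poorer PFS result than a simple explicit one.

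**What to change.** - **SAP 5.2.2 and Protocol 12.4:** replace the statement that the patient is deemed progressed with *counted as a non-responder for ORR and as no clinical benefit for CBR*. The patient stays in the population.
- **SAP 4.2.3.2:** add that stopping study drug for an AE is not by itself a PFS event, and that a patient with no post-baseline scan and no death is censored at first dose. Death remains an event.

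The cost is two SAP edits and one protocol sentence, with no new data. They should be settled before database lock, when patients are assigned to populations (SAP 5.2).

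The downside is that PFS loses a conservative failure coding for early toxicity stops, and censoring these patients assumes their dropout is unrelated to prognosis. Last-contact censoring of patients who do have scans is a separate matter that these edits leave unchanged.
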